estimate the random effects associated with each level of nesting. If any of these are statistically not significantly different from zero, we will drop these from the specification, prior to testing of the hypotheses. Note further, that as described below, the Hierarchical Linear Model (HLM) to be used to test our hypotheses is described with only a linear term in time. During our examination of the levels of nesting we will also examine the trajectories (again blind to condition) to ascertain any higher order polynomial trends in the data. For example, if a quadratic term in time is found to have significant variance over individuals, we will include the quadratic term in the HLM. The model as presented below does not show the nesting of 28-day periods within assessments and only shows the linear term of the growth model in an effort to keep the notational clutter to a minimum.

Analysis. Hypothesis 1 will be tested using hierarchical linear models (HLM) (Bryk & Raudenbush, 1992) to estimate the growth curve of drug use post-randomization. The trajectory of change in drug use will be compared between BSFT and TAU. HLM controls for the nesting of both repeated observations within the same adolescent over time and the nesting of adolescents within a CTP and further allows for a single test of the effect of the intervention across multiple times and sites (see planned post-hoc tests, below). HLM allows for the flexible inclusion of adolescents who may have missed assessments, and allows for non-linearity of the trajectory of change in the dependent measure. Finally, HLM allows us to consider treatment site as a random effect and to examine variability in treatment effects across sites. The treatment of site as a random effect is in keeping with the mission of the CTN to test the general applicability of proven treatments in real world settings. Thus, it is a goal of this protocol to show that BSFT will be efficacious in the population of community treatment providers, not just the community treatment providers in the sample (which a fixed effect specification would imply). This specification of the test actually compares the effectiveness of BSFT relative to the average effectiveness of TAU in the sites in the protocol. The analysis will include as a covariate referral from an institution for the treatment of drug.

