HLM conceptualizes the growth curve as separate equations for the intercept and another equation or other equations (if more than linear change is examined) for the slope, though both (all) are estimated jointly. With the addition of treatment site as a random effect, this model is a three level HLM model. These three levels are associated with 1) time, 2) individual and 3) site. There is an additional level, or random effect associated with the nesting of 28-day periods within an assessment. As noted above, prior to testing hypotheses, in an analysis blind to condition, we will fit these 4 different levels (and additional polynomial terms). If any of the random components, or polynomial terms are not significantly different from zero, we will drop them from the model. Note that in the presentation that follows, we just present the substantive levels of the individual and omit the higher order polynomial terms to focus the exposition on the substantive issues (the growth curve and site variation). To facilitate interpretation of the growth curve, time will be centered on the 4-month post-randomization assessment (T4). Thus, the intercept term represents the difference between the two conditions immediately post intervention. If the expected ordinal nature of the outcome measure results in sufficient deviation from normality a Poisson link function will be used.

10.2.1 Level 1

For Hypothesis 1, the time path of percentage of days having used drugs in 28-day periods will be estimated and the growth trajectory will be parameterized to be a function of BSFT intervention status. Additional predictors will be the stratification variables specified in the urn randomization and the other variables, described under the heading randomization (see section 10.1.1) and any baseline variables found to predict the occurrence of missing data. The growth curve analysis will include the times after baseline only, and baseline value of the dependent measure will be included as a covariate (i.e. an analysis of covariance parameterization). The presentation below does not include the baseline value of drug use or

these other additional covariates, to ease the exposition. As mentioned this is a three-level HLM model. Level 1 describes the trajectory over time for an individual participant:

Level 1

$$y_{ijt} = \pi_{ij0} + \pi_{ij1} \cdot a_{ijt} + \varepsilon_{ijt},$$

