Therapist differences might also be an important source of variability in outcomes. In fact, the effect of participants being nested within therapist might be modeled similarly to the site effect in the planned primary analysis. In planned post-hoc analyses we will explore the effect of adding therapist as a fourth nesting factor (between participants and sites). We will also see if there are particular therapist characteristics (e.g., training, experience) or therapeutic processes (e.g., alliance) that explain this source of variance.

Further analyses will establish the effect-sizes within each of the sites and examine whether patient characteristics differed by site, and thus might explain any observed variability in effect size across sites. As stated above, the primary test of the effectiveness of BSFT is an average of the effectiveness across sites. Whereas it is not expected, it is possible that a site or sites might have TAU results that are more effective than BSFT (a negative effect) but still on average across sites show BSFT to be more effective. This planned post-hoc analysis will document that this is or is not the case.

Analyses of alternative formulations of the drug use outcome variable will be explored to provide evidence for planning of future drug abuse trials with adolescents. Specifically we will look at various ways of weighing drug use days by the number of drugs used in the day. This variable may be more sensitive to poly-drug use, however standard psychometrics including reliability and validity are not presently available.

Finally, whereas the primary outcome in this proposal is related to the functioning of the participating adolescent, family therapy modalities also are likely to affect all family members. Thus a post-hoc analysis will be done examining the changes in parent alcohol and drug use using the ASI done on the parent.

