From examining multiple configurations, we propose that we need 8 sites with approximately 60 participants per site, on average. This results in a total sample size of 480. Because we believe that recruitment rates are relatively consistent across the 8 outpatient sites, we estimate an effective n of 57. Thus, there is a 3 subject per site penalty for allowing the sites to vary in size. With our proposed sample configuration ($n=60$, $J=8$, effective $n=57$), there is nearly 75% power to uncover main effects of treatment with an effect-size of .45 and relatively small site by treatment variability.

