10.4.1 Main Effect of Treatment (Treatment X Time interaction)

Figure 4 (prepared using software provided by [name]) shows the expected power to uncover a significant overall treatment effect when there are 8 sites ($J=8$), the average treatment effect is .45 ($\delta=.45$) and the variability in this effect size is either small, moderate or large ($\sigma_{\delta}^2=.10$, and .15; as coined by Raudenbush & Liu, 2000). As can be seen in the graph, at the point of 57 subjects per site, power is 87% with small site variability, 75% with moderate site variability, and 64% with high site variability.

FIGURE 4. POWER

[figure not shown]

As can be seen in the graph, site variability in effect-sizes may have a substantial effect on power. If we compare the power calculations above with a simple repeated measures power analysis, we see that if there is no variability in effect-sizes across sites, that we have over 80% power to uncover a considerably smaller standardized effect size. We have used the program described in Hedeker, Gibbons, & Waternaux (1999) to calculate power in the case with no variability of effect-size across sites. In this case, there is over 90% power to uncover a Condition X Time interaction with an effect-size of .25 at the last time of assessment. This estimate assumes 28% attrition over the 12-month post-randomization period, a linear growth curve and minimal residual correlation across time ($\rho = .1$). Power actually increases as the correlation of measures across time increases. It is not uncommon for measures such as those used to test the hypotheses in the trial to show correlations across time in the range of .2 to .4, so power may be better than described here. Clearly, if site variability is smaller than the estimates in the graph above, there is substantially more power. On the other hand, if site variability is higher than the estimates in the graph above, there is substantially less power.

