13.0 DISCONTINUATION OF STUDY Interim Analyses

This trial does not meet any of the conditions listed in the Data Safety Monitoring Boards SOP that would require a planned interim analysis for efficacy:

- 1) the trial does not involve over 1000 participants
- 2) treatment is under 6 months in duration
- 3) death or other serious adverse events are not included as efficacy endpoints
- 4) published information supports the efficacy of the experimental treatment
- 5) pharmacological treatment is NOT included in the protocol

There are other factors related to this effectiveness trial's design that lessen the need for an a-priori planned interim analysis. First, this is not a blinded study. Second, the experimental treatment is being compared to the treatment as usual at each site and these sites are established drug treatment centers using established treatment approaches. It is thus highly unlikely that there will be such large effect-sizes that the trial would be stopped early due to the overwhelming efficacy of the proposed experimental treatment. On the other hand, the established research on the proposed experimental treatment does provide substantial evidence of its efficacy in treatment of adolescent problem behavior and drug abuse, making it unlikely that there would be overwhelming efficacy of the treatment as usual, over the experimental treatment. Third, the proposed estimation strategy for this trial directly accounts for the expected variability in effect size across sites by including a random effect for the treatment effect. Note that this variability is expected to be higher than might be seen in efficacy trials due to the variability in treatment as usual across sites. The stability of the statistical model is directly affected by this estimate of variability. It is generally felt that at least 5 sites are necessary to achieve a stable estimate of variability (Brown & Prescott, 1999). Because the primary test includes an interaction by modality (residential vs. outpatient), this would require at least 5 sites in each modality to generate stable estimates of the treatment effect.

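### The blind rule to drop non-significant random effects protects no component, so it can delete the site-level treatment variance on which the primary test, the power model and section 13.0 rely

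*Protocol*

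**What the plan says.** Protocol 10.2 describes four levels: 28-day periods within assessments, assessments within adolescents, adolescents, and sites. Before any hypothesis test the random effects at each level are estimated without knowledge of treatment arm. Then: "If any of these are statistically not significantly different from zero, we will drop these from the specification, prior to testing of the hypotheses". The analysis paragraphs of 10.2 repeat the rule more broadly: "If any of the random components, or polynomial terms are not significantly different from zero, we will drop them from the model". Neither statement exempts the site level or the site-by-treatment terms.

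Other parts of the protocol depend on those terms:
- 10.2 makes site random because "it is a goal of this protocol to show that BSFT will be efficacious in the population of community treatment providers", and rejects the fixed-effect reading.
- 10.2.3 gives the BSFT effect on the intercept and on the slope its own site-specific error (u1j0 and u1j1) and carries both into the combined equation.
- 10.4 and 10.4.1 base power on 8 sites with an effect that varies between sites.
- 13.0, arguing against a planned interim efficacy analysis, says that the estimation strategy "directly accounts for the expected variability in effect size across sites by including a random effect for the treatment effect", and expects that variability to be larger than in efficacy trials.

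**The concern.** A non-significant variance estimated from 8 sites is weak evidence that the variance is zero. A rule that deletes on non-significance therefore tends to delete real variance.

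The blinding adds a second problem. u1j0 and u1j1 multiply the BSFT indicator, so a fit without treatment arm cannot estimate them. Either they disappear when the site level is dropped, never having been tested, or the rule cannot be applied to them as written. The protocol does not say which.

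If they go, the standard error of the primary effect is too small whenever the effect truly varies between sites. The inference also shrinks to the sampled programs, which 10.2 says is not the aim.

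**Working it through.** **Inputs.** J = 8 sites, 60 per site on average, effective n = 57, standardised effect .45 (10.4, 10.4.1). Site-by-treatment variances σ² of .10 and .15 are printed in 10.4.1. The small value is not legible in the text, and .05 is assumed. Two-sided 5% testing is assumed. The outcome has unit within-arm variance, and each site is summarised by its BSFT-minus-TAU contrast, with variance σ² + 4/n.

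**The plan's own figure.** Power is taken from a non-central F(1, 7) with λ = J × .45² / (σ² + 4/n). At n = 57, 4/n = .0702:

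| σ² | λ | Power computed | Power stated |
|---|---|---|---|
| .05 | 1.62/.1202 = 13.5 | 88.1% | 87% |
| .10 | 1.62/.1702 = 9.5 | 75.4% | 75% |
| .15 | 1.62/.2202 = 7.4 | 64.5% | 64% |

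All three agree within 2 points, so this is the protocol's planning model. It keeps the random treatment effect and uses J − 1 = 7 degrees of freedom.

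**Type I error, true mean effect zero, n = 60 (4/n = .0667).** Order of results: σ² = .05 / .10 / .15.

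1. *Terms always kept, t test on 7 df:* 5.0% throughout.
2. *Terms always dropped:* size = 2Φ(−1.96 × √[(4/n)/(σ² + 4/n)]). At σ² = .05 the root is √(.0667/.1167) = .756, and 2Φ(−1.48) = 13.8%. The three results are 13.8 / 21.5 / 27.7%.
3. *Direct pre-test of σ² (treatment arm known), 400,000 simulated trials per setting.* The boundary-corrected likelihood-ratio statistic is 7(x − 1 − ln x), where x is the observed variance of the contrasts divided by 4/n, with critical value 2.706. It keeps the term in 28 / 54 / 70% of trials, and size is 10.0 / 10.5 / 9.4%. A Q pre-test gives 9.4 / 9.7 / 8.6%.
4. *Blind likelihood-ratio screen of site means, with the BSFT-by-site term kept or dropped along with the site level.* The coding is 0/1 as in 10.2.2, with u0 and u1 independent. The site-intercept variance is not in the protocol, so a range is shown:

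| Site-intercept variance | σ² = .05 | .10 | .15 |
|---|---|---|---|
| 0 | 11.0% | 11.9% | 10.8% |
| .02 | 7.9% | 8.5% | 8.1% |
| .05 | 6.1% | 6.4% | 6.4% |
| .10 | 5.3% | 5.5% | 5.4% |
| .20 | about 5.1% | about 5.1% | about 5.1% |

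5. *Wald Z screen.* With 8 balanced sites, Z = √(7/2) × (1 − v/S²), where S² is the observed variance and v its sampling part. Z cannot reach √3.5 = 1.87, which is below 1.96. A two-sided 5% Wald screen therefore always drops the component, and the figures in item 2 apply. Over the same range of site-intercept variances, Wald screens give about 7% (one-sided, variance .20) to 28%.

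The results in item 4 depend on the coding. If the treatment effect varies independently of the site's average level, the blind screen carries no information about σ². With no variance in site averages, a Q screen then gives 12.9 / 20.0 / 25.7% (n = 57).

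For very small effect variance the problem fades. At σ² = .02 the direct pre-test gives 7.1 to 7.7% (n = 57), and at zero there is no inflation.

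**The case against.** The strongest reply is that the rule was meant only to prune nuisance levels. 10.2 motivates it by levels whose variance is close to zero, the screen is blind and works level by level, and 10.2.3 and 13.0 treat the random treatment effect as part of the model. On that reading u1j0 and u1j1 are never touched and there is no inflation. The reading is reasonable, but the text does not secure it: 10.2 speaks of any random component and exempts none.

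A reader might go further and infer three things that the protocol does not support:

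- *That the rule roughly doubles the false-positive rate in general.* That figure comes from a direct pre-test of the treatment contrast, or from a blind likelihood-ratio or Q screen when site averages hardly differ. The protocol expects varied populations and varied usual care (4.1, 5.2.2, 13.0). With site-intercept variance of .10 or more, a blind likelihood-ratio screen leaves the error near 5%.
- *That 8 sites cannot detect the variance.* A likelihood-ratio test detects it in 54% and 70% of trials at the two printed values. The right word is unreliable, except for the two-sided Wald Z.
- *That a therapist effect must move into the primary model.* Therapists are randomised to one arm within site, about 4 to 8 per site (5.3), and 10.2.6 leaves their nesting to post hoc work. They add 2 × ICC/m to the contrast variance, with m therapists per arm. At an assumed ICC of .05 and m = 2 that is .05. The ICC is not in the protocol, and retained BSFT-by-site terms absorb most of this variance.

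**Conclusion.** The concern holds as a conflict within the protocol that bears on the primary test. Section 10.2 permits deletion of the component that the rest of 10.2, 10.2.3, 10.4 and 13.0 rely on, after a screen that cannot assess the BSFT-by-site part and is unreliable for the site part.

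The size depends on how the rule is read and which test is used: about 5% if the terms stay or site averages clearly differ under a likelihood-ratio screen, about 9 to 12% in the middle cases, and 14 to 28% if the terms are dropped. These figures rest on σ² of .05 (assumed), .10 and .15, a site-level summary rather than the full growth model, balanced sites, and an unstated site-intercept variance shown as a range. They do not show that the test will be inflated, only that the protocol as written does not prevent it.

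**What to change.** State in 10.2, before any unblinded analysis:
- The site random effects and the BSFT-by-site random effects, on intercept and slope, stay in the primary model whatever their estimate or significance.
- The BSFT effects are tested with small-sample degrees of freedom, for example J − 1 or Kenward-Roger.
- The blind screen applies only to the polynomial time terms and to the level for 28-day periods within assessments.

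Therapist nesting can remain a planned post hoc or sensitivity analysis.

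The cost is a change of wording, plus a wider interval if the site variance is truly zero. At equal standard error the critical value rises from 1.96 to 2.36 (t, 7 df), and 2.36/1.96 = 1.20, about 20% wider. The power model in 10.4 already accepts this.

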10.1.1 Overview of Analysis

Testing of Distributional Assumptions. Statistical tests for univariate and multivariate normality (tests of skew & kurtosis) as well as visual inspections of the empirical distributions will be conducted. For all hypotheses residuals from the statistical analysis will be examined to determine that distributional assumptions are met. If these analyses show significant deviations non-parametric, or non-normal based versions of the proposed hypothesis tests will be devised. For example, for count data of small range, Poisson regression is indicated (Koch, Atkinson & Stokes, 1986).

Sampling and Generalizability. To establish comparability for subsequent analyses, comparisons of demographic characteristics between the following groups of participants will be conducted: participants who agree to participate (sign consent), and participants who are randomized. Analyses will also document the reasons for non-eligibility and reasons for non-participation of those eligible. Further comparisons will be made to the groups that remain in the study through various assessment times as described below in Missing Data and Attrition.

Urn Randomization. Randomization will be conducted separately by the CTP using a telephone call-in procedure developed by the Veteran's Affairs. This procedure uses an urn randomization program to increase the likelihood that treatment groups are balanced on two characteristics: Ethnicity/ race (Hispanic, African-American, other) and Level of Drug Use (any drug diagnosis other than alcohol or tobacco, no drug diagnosis) at baseline. This will ensure balance across the two treatment conditions.

All variables included as factors in the urn program will be included as covariates in the primary test of the intervention effectiveness. In addition, age, gender, baseline levels of psychiatric co-morbidity status (no comorbidity, externalizing disorder/s, internalizing disorder/s, internalizing and externalizing disorders), primary drug of abuse, family type and family-peer functioning will be controlled due to their anticipated relationship to most of the outcomes.

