10.2 Primary Outcome and Hypothesis

Hypothesis 1. BSFT will be significantly more effective than TAU in reducing adolescent drug abuse, defined as the percentage of drug use days in 28-day periods.

Outcome Variable. The outcome variable for this hypothesis is the percentage of days of drug use within a 28-day period. This variable will be constructed from the Timeline-Follow-back instrument and will be measured as the sum of the number of days with positive use in 28-day increments (there are thirteen 28-day periods in this design, B1 and T1-T12). Periods in which the participant is in a restricted environment will be flagged in the database, but will be included in the primary analysis. If there is missing information on the time-line follow-back within a 28-day period, the percentage will be calculated as the percentage of available days in that period, as long as not more than 14 days are missing. There is a chance that data collected at the same assessment point are more related than data collected across assessment points. Our data analysis strategy exploits the nested structure of our data. Thus, in this protocol, 28-day measures of drug use are nested within 13 assessment points, these assessment points are nested within individuals, individuals are nested within community treatment providers. The statistical model, as defined below, accommodates these different nesting factors. From our experience, in models with many levels of nesting, it is not uncommon for some of the random effects associated with these levels to have close to zero variance. Thus, our strategy will be to first examine the trajectories (blind to the condition assignment), and to

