where y_{ijt} , a_{ijt} , and ε_{ijt} , are % of drug use days, time, and a random (or error) term, respectively, for person i , in CTP j , at observation occasion t . The variable a_{ijt} will be measured as time from assessment point (T4), which occurs four months post randomization. The variables π_{ij0} and π_{ij1} are the intercept and slope of drug use, respectively for person i , in CTP j .

10.2.2 Level 2

The Level 2 model describes the individual intercept, π_{ij0} , and the individual slope term, π_{ij1} as a function of *BSFT*:

Level 2

$$\pi_{ij0} = \beta_{0j0} + \beta_{1j0}BSFT + r_{ij0},$$

$$\pi_{ij1} = \beta_{0j1} + \beta_{1j1}BSFT + r_{ij1}.$$

The *BSFT* variable is a 0-1 or dummy-coded variable that is coded 1 if the participant is receiving BSFT, and 0 otherwise. Given this coding of the *BSFT* variables, β_{0j0} and β_{0j1} are the intercept and slope, respectively, for participants who are in the TAU condition. The parameters, β_{1j0} and β_{1j1} , are the increments to the intercept and slope of the TAU participants, (β_{0j0} and β_{0j1} , respectively), for participants receiving *BSFT* at treatment site j (i.e. intercept for *BSFT*= $\beta_{0j0} + \beta_{1j0}$ and slope for *BSFT*= $\beta_{0j1} + \beta_{1j1}$). Finally, r_{ij0} and r_{ij1} are person-specific random terms for the intercept and slope.

10.2.3 Level 3

The Level 3 model incorporates the variability across treatment sites into the coefficients of the Level 2 model.

Level 3

$$\beta_{0j0} = \gamma_{000} + u_{0j0},$$

$$\beta_{1j0} = \gamma_{100} + u_{1j0},$$

$$\beta_{0j1} = \gamma_{001} + u_{0j1},$$

$$\beta_{1j1} = \gamma_{101} + u_{1j1},$$

At level 3, the u terms are site-specific error terms. In the absence of covariates, γ_{000} is the grand mean of TAU at T4 (immediately post intervention) and $\gamma_{000} + \gamma_{100}$ is the mean of BSFT at T4 and γ_{100} is the treatment effect of BSFT at T4. Again, in the absence of covariates, γ_{001} is the rate of change from T4 to T12 for TAU and $\gamma_{001} + \gamma_{101}$ is the rate of change of BSFT from T4 to T12 and γ_{101} is the treatment effect of BSFT at T4.

Whereas the model to be tested is conceptualized in 3 distinct levels, it is actually estimated as one single equation with multiple fixed and random effects. Substituting in the various equations gives:

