$$y_{ijt} = [(\gamma_{000} + u_{0j0}) + (\gamma_{100} + u_{1j0})BSFT + r_{ij0}] + [(\gamma_{001} + u_{0j1}) + (\gamma_{101} + u_{1j1})BSFT + r_{ij1}] \cdot a_{ijt} + \varepsilon_{ijt}$$

or,

$$y_{ijt} = [(\gamma_{000} + \gamma_{100}BSFT) + (\gamma_{001}a_{ijt} + \gamma_{101}BSFT * a_{ijt}) + (\varepsilon_{ijt} + u_{0j0} + u_{1j0} * BSFT + u_{0j1} * a_{ijt} + u_{1j1} * BSFT * a_{ijt} + r_{ij0} + r_{ij1} * a_{ijt})]$$

This model will be estimated using either SAS Proc Mixed (or Proc NLMixed if a non-linear link function is necessary).

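### The Poisson fallback for the primary outcome ignores the upper bound and the 14-to-28-day denominator, and its standard errors depend on whether percent or days are entered

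*Protocol*

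**What the plan says.** Protocol section 10.2 defines the primary outcome in two ways. First: "The outcome variable for this hypothesis is the percentage of days of drug use within a 28-day period". Then the same variable "will be measured as the sum of the number of days with positive use in 28-day increments". When days are missing, "the percentage will be calculated as the percentage of available days in that period, as long as not more than 14 days are missing", so the denominator runs from 14 to 28. The Level 1 equation (10.2.1) settles on the percentage for the linear model: its three terms "are % of drug use days, time, and a random (or error) term, respectively".

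For non-normality, section 10.2 says: "If the expected ordinal nature of the outcome measure results in sufficient deviation from normality a Poisson link function will be used". The software is then "Proc NLMixed if a non-linear link function is necessary". No offset, number of trials, upper limit or dispersion parameter is mentioned.

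Section 10.1.1 allows non-parametric or other non-normal tests in general. Its one example is that "for count data of small range, Poisson regression is indicated".

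Two further statements in section 10.2 matter. It describes a random effect for 28-day periods within assessments, in addition to time, person and site. It also says that random components not significantly different from zero are dropped before the hypotheses are tested.

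**The concern.** A percentage of available days has a floor, a ceiling and a known number of trials. It is not ordinal, and it does not fit the protocol's own description of where Poisson belongs. A Poisson model allows any non-negative value, sets the variance equal to the mean in whatever unit is entered, and has no place for the denominator unless one is supplied.

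The fallback would carry the test of Hypothesis 1. Two analysts following the text could enter 0–100 or 0–28, obtain nearly the same coefficients, and report different standard errors and p-values.

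**Working it through.** **The plan's own figures.** The protocol gives no number for the fallback. Its power figures (section 10.4.1: 87%, 75%, 64%) come from a normal outcome. With J = 8, effective n = 57, δ = 0.45 and λ = Jδ²/(σ² + 4/n) in a noncentral F(1, 7), two-sided 5%, I get 88.1%, 75.4% and 64.5% for σ² = 0.05 (assumed, since the value for small variability is not in the text), 0.10 and 0.15. They agree within about a point, but they do not bear on the fallback.

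**Inputs.** m = 14 to 28 available days and the unit 0–100 or 0–28 (section 10.2); 480 participants ("we propose that we need 8 sites with approximately 60 participants per site, on average") and 12 follow-up periods. The protocol gives no mean, SD or share of zeros for drug use, so the use levels p below are illustrations.

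**1. Upper bound.** At p = 0.9 and m = 28, the Poisson mean is 25.2 days and P(Y > 28) = 0.249. For independent days, Poisson variance on days is 1/(1 − p) times the binomial variance: 1.33 times at p = 0.25, 2 times at 0.5, 10 times at 0.9.

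**2. Denominator.** The binomial variance of the percentage is 10⁴p(1 − p)/m. At p = 0.25 it is 67 for m = 28 and 134 for m = 14. Poisson on the percentage assumes 25 for both, which is 0.37 and 0.19 of those values.

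**3. Unit of entry.** Multiplying y by c divides the Poisson model-based standard error by √c. From days to percent, c = 100/28 = 3.57 and √c = 1.89.

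**4. Size without absorbing random effects, percent entry.** For independent days the variance-to-mean ratio is φ = 3.57(1 − p): 3.2 at p = 0.1 and 2.5 at p = 0.3. Actual size is 2[1 − Φ(1.96/√φ)], which gives 0.27 and 0.22.

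**5. Standard errors with random effects.** Simulated data: 480 × 12, 20% of periods with 14–27 available days, between-person SD 1.5 on the logit scale, no site effects. *Clustered* means added beta dispersion. All inputs are assumptions; the slope fits average 6 replicates.

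| Poisson fit | Term | SE, percent | SE, days | Ratio |
|---|---|---|---|---|
| No random effects | treatment | 0.0072 | 0.0137 | 0.53 |
| Random intercept | BSFT-by-time | 0.0017 | 0.0032 | 0.53 |
| Random intercept | BSFT at T4 | 0.105 | 0.102 | 1.03 |
| Intercept and slope | BSFT-by-time | 0.0082 | 0.0073 | 1.12 |
| Intercept and slope | BSFT at T4 | 0.106 | 0.101 | 1.05 |
| Intercept and slope, clustered | BSFT-by-time | 0.0165 | 0.0133 | 1.24 |
| Intercept and slope, clustered | BSFT at T4 | 0.148 | 0.127 | 1.17 |

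A ratio of 0.53 is 1/1.89. With the slope kept, the direction reverses.

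**6. Size with the period-level effect.** Null data with similar assumed inputs, 240 replicates, no person slopes or site effects. Rejection of BSFT-by-time at nominal 5%:

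| Poisson fit | Percent | Days | Percent, clustered | Days, clustered |
|---|---|---|---|---|
| Random intercept only | 19% | 2% | 58% | 28% |
| Plus period-level effect | 7.5% | 2% | 6% | 7% |

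The Monte Carlo standard error at 5% is √(0.05 × 0.95/240) = 1.4 points. With the period-level effect, standard errors still differ by unit by about 10%, or 40% when clustered. The T4 effect was rejected in about 5–7% of runs in every setting.

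**The case against.** The strongest reply is that the protocol already has the remedy for overdispersion. With about one 28-day period per assessment, the period-within-assessment effect acts as an observation-level term, and step 6 shows that it removes most of the size inflation. This stands, and it limits the claim. It is not a full answer, because the effect is subject to the drop rule. If the screening is done under the normal model, that effect is confounded with the residual and could be lost before the Poisson model is fitted.

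A second reply is that the count wording in section 10.2 and the small-range example in section 10.1.1 point to Poisson on 0–28 days, which is conservative when days are independent. This is a fair reading, but the model equation says percent. Step 6 also shows 28% rejection on days when use is clustered and only a random intercept is kept. An offset for available days would settle the unit but not the upper bound.

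Third, the term may mean only a log link with normal errors. The unit problem would then disappear, but the bound and the unequal precision would remain.

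Fourth, offsets and dispersion terms are commonly left to the SAP, and section 10.1.1 does not bar other families. Silence on those details is therefore not the fault. The fault is that section 10.2 names a specific family for this outcome, and that family does not fit it.

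**Conclusion.** The point holds for the choice of family. Poisson mishandles the ceiling and the denominator at any unit, and the text leaves the unit open. The effect on inference depends on which random effects remain:

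- **Both the random slope and the period-level effect absent or dropped:** the BSFT-by-time standard error changes by a factor of 1.89 with the unit. On percent entry the size is about 22–27% at 10–30% use with independent days.
- **Either kept:** the standard errors differ by roughly 5–40%, in either direction, under the assumed inputs.
- **T4 effect, the other half of the primary test (section 10.2.4):** much less affected when a person random effect is kept.

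A reader might infer that p-values for the primary effect are arbitrary, or that the primary test has a size near one in four. The documents do not support this, because the model as written includes both the person slope and the period-level effect.

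A reader might also infer that some 5,760 observations (480 × 12) with many zeros make Poisson in effect the primary model. This cannot be established either. Section 10.1.1 combines tests with visual inspection and residual checks, section 10.2 sets no threshold for sufficient deviation, and no outcome distribution is given.

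**What to change.** Replace the Poisson sentence in section 10.2 with a binomial (logit) or beta-binomial mixed model for days used out of days available in each period. Keep the person and site random effects, and add a person-by-period effect for overdispersion that is exempt from the drop rule. Delete the word *ordinal*. State the outcome once, as days used over days available, and report the model-based mean percentage of days by arm.

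This is a wording change, best made before unblinding, and it runs in the non-linear mixed procedure already named. The cost is that the raw coefficient is an odds ratio and must be converted back to percentage of days.
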